### **6.3.5. Physical Examination**

The number and percent of patients with clinical findings at each visit will be summarized following Pfizer Reporting Standards.

### **6.3.6. BMI and mBMI**

BMI and mBMI values at each visit and change from baseline will be presented in summary tables and data listings. Descriptive statistics will be provided by visit.

### **6.4. Other Endpoints (Efficacy Endpoints)**

- Change from Baseline in cardiac troponin I

The analysis method described in [Section 5.2.1](#) will be followed, i.e. the basic summary statistics will be calculated by analysis visit. The estimates over time will be plotted graphically.

- Change from Baseline in New York Heart Association (NYHA) classification

An increase or decrease in NYHA classification relative to baseline will be summarized using a shift table at each time point post-baseline.

### **6.5. Subset Analyses**

All efficacy, safety, quality of life, and PD endpoints (including TTR concentration, percent stabilization [as PD continuous measures], the proportion of participants who achieve TTR stabilization [ie, who has been stabilized, also called responder in TTR stabilization] and its 95% confidence interval [as PD categorical measure]) analyses will be repeated by NYHA baseline classification (I/II or III+). PD endpoints analyses will be repeated by TTR genotype (wild-type or variant), if the sample sizes for both subsets allowed.

### **6.6. Baseline and Other Summaries and Analyses**

#### **6.6.1. Baseline Summaries**

Baseline variables will be summarized descriptively. Continuous variables will follow methods in Section 5.2.1. Categorical variables will follow methods in [Section 5.2.2](#). Medical history will be listed by participant.

#### **6.6.2. Study Conduct and Participant Disposition**

The end of treatment subject disposition will be shown. Frequency/counts will be provided for subject discontinuation(s) and completion.

#### **6.6.3. Study Treatment Exposure**

The duration of treatment will be calculated as: data of the last dose – date of the first dose + 1. Any missed doses/off drug period will be ignored in the duration calculation. The treatment exposure will be defined as the number of days that participant took the study drug (gaps not counted). Both will be summarized in following categories (days): 1, 2-30 ( $\leq$ 1 month), 31-90 (1-3 months), 91-180 (3-6 months), 181-270 (6-9 months),  $\geq$ 271 (9-12 months).

Since study treatment should be taken once daily, study drug compliance will be calculated for each patient as: treatment exposure / treatment duration  $\times$  100. Compliance will be listed as both a continuous and categorical (<80%,  $\geq$ 80%) endpoint.

#### 6.6.4. Concomitant Medications and Nondrug Treatments

Concomitant medication usage by medication type will be tabulated using the WHO-Drug dictionary and listed following Pfizer Data Standard. Nondrug treatment will be listed as well.

#### 6.7. Additional Analyses Depicting COVID-19 Pandemic Impact

In order to report the impact of COVID-19 on clinical trial populations and study data, the following listings and summaries will be produced:

- Listing of subjects with alternative facility or telehealth visits due to COVID-19 pandemic
- A separate summary table solely for subject discontinuations from investigational product and withdrawal from study related to COVID-19 pandemic, if any, will be provided
- Protocol deviations related to COVID-19 pandemic will be summarized and listed separately. Both important and non-important PDs related to COVID-19 pandemic will be reported
- COVID-19 related AEs, if any, will be reported separately

### 7. INTERIM ANALYSES

No interim analysis will be conducted for this study. As this is an open-label study, the sponsor may conduct unblinded reviews of the data during the course of the study for the purpose of safety assessment, facilitating PK/PD modeling, and/or supporting clinical development.

#### 7.1. Introduction

Not applicable.

#### 7.2. Interim Analyses and Summaries

Not applicable.

### Appendix 1. Data Derivation Details

#### Appendix 1.1. Definition and Use of Visit Windows in Reporting

To maximize the use of all available data, the analysis visit windows are expanded. For endpoints with post-baseline assessments at Month 1, 6 and 12 (except PK endpoints), the analysis windows are defined in below table. The study day will be calculated as: date of assessment/collection – date of the first dose + 1. If two or more visits/observations fall into the same window, the visit / observation closest to the target day should be used in the analyses. If there is a tie, the later visit should be used. Note: for ECG and Echocardiogram, the central laboratory reading data takes priority. For NT-proBNP, TNI and RBP, only the central laboratory reading data are included in analysis.

Visit Label	Target Day	Definition [Day Window] - Lower	Definition [Day Window] - Upper
-------------	------------	---------------------------------	---------------------------------

Baseline	1	Day 1 = date of first dose of study treatment taken in the study  Prior to first dose of study treatment taken in the study	
Month 1	31	16	105
Month 6	181	106	270
Month 12	361	$\geq 271$ (Note: Set upper at Day 375 for PD endpoints)	

For endpoints with post-baseline assessments only at Month 6 and 12, the analysis visit windows are defined as below.

Visit Label	Target Day	Definition [Day Window] - Lower	Definition [Day Window] - Upper
Baseline	1	Day 1 = date of first dose of study treatment taken in the study  Prior to first dose of study treatment taken in the study	
Month 6	181	91	270
Month 12	361	$\geq 271$	

For PK, tafamidis concentrations will be measured at Month 1 pre-dose and 3 hours ( $\pm 1.5$  hours) post-dose; Month 6, 7 hours ( $\pm 2.5$  hours) post-dose; Month 12, 1 hour ( $\pm 30$  minutes) post-dose. The PK sampling windows are defined in below table. The sampling time window will be calculated as: time of sample collection – time of dosing of most recent study treatment.

Visit Label	Planned Time Post Dose (hours)	Definition [Time Window] – Lower (hours)	Definition [Time Window] – Upper (hours)
Month 1	0 (Pre-dose)	Prior to dosing of study treatment on the sample collection day	
Month 1	3	1.5	4.5
Month 6	7	4.5	9.5
Month 12	1	0.5	1.5

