Documentation of vital status		X	X	X	X	X	X	
Record time of dosing		X	X		X		X	
Record dosing adherence			X		X		X	
Dispense investigational drugs		X	X		X			

- Visits, if applicable, are typically defined with respect to the Baseline visit and in accordance with expectations on the standard of care and/or required procedures for the study.
- Systolic and diastolic blood pressure (semisupine at least 5 minutes prior to assessment), pulse rate, respiratory rate and body temperature
- Biopsy or radionuclide bone scintigraphy (99mTc-PYP) for amyloid documentation must be performed at Screening or have been performed and documented within 5 years of enrollment. If greater than 5 years, biopsy or radionuclide bone scintigraphy (99mTc-PYP) must be repeated at the investigative site.
- Refer to [Appendix 4](#) for Contraceptive Guidance and Collection of Pregnancy Information.
- For women of childbearing potential. Refer to [Appendix 4](#) for Woman of Childbearing Potential (WOCBP).
- For those absence of a variant TTR genotype, absence of radionuclide bone scintigraphy (99mTc-PYP) and presence of amyloid deposits in biopsy tissue.
- Repeat not required if there is documentation of genotyping result confirming the TTR gene mutation within 5 years of enrollment.
- TTR stabilization and TTR concentration: baseline (Day 1) sample: collect pre-dose during the clinic visit. Month 1 sample: collect pre-dose and at 3 hours (±1.5 hours) post-dose. Month 6 sample: collected at

Procedure/ Assessment	Screening	Baseline visit	Month a					
			1 (±1 wee k)	3 (Tel eph one visit ±2 wee ks)	6 (±2 week s)	9 (Tel eph one visit ±2 wee ks)	12 (±2 weeks) (or within 2 weeks after End of Treatment)	Post- treatment follow-up (28+7 days after last dose)
	Day-45 to Day 0	Day 1						

7 hours (±2.5 hours) post-dose. Month 12 sample: collect at 1 hour (±30 minutes) post-dose, or End of Treatment sample: collect at time during the clinic visit. Please refer to [Section 8.6](#) for details.

- i. Tafamidis concentrations: Month 1 tafamidis concentration sample: collect pre-dose and at 3 hours (±1.5 hours) post-dose; Month 6 tafamidis concentration sample: collect at 7 hours (±2.5 hours) post-dose; Month 12 sample: collect at 1 hour (±30 minutes) post-dose, or End of Treatment sample: collect at time during the clinic visit. Please refer to [Section 8.5](#) for details.
- j. Kansas City Cardiomyopathy Questionnaire (KCCQ) should be completed before the EQ-5D-5L.

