#### **6.1.1. Administration**

Participants will swallow the investigational product whole, and will not manipulate or chew the investigational product prior to swallowing and taking the capsules with a glass of water. Participants will be instructed to dose at a consistent time of day. Participants will be instructed to start taking their medication each day in the morning (AM dosing); however, it is permitted for participants to take his/her medication in the afternoon or evening prior to a clinic visit (eg, the Month 6 visit) when the timing of PK sample collection is prohibitive for adherence with AM dosing. Participants should not take an extra dose of medication in the event that a dose from a previous day is missed and should resume dosing capsules per day from an individual row on the study medication at the next planned dosing time. Similarly, if multiple doses are missed in succession, the participant should resume dosing at the next planned dosing time without taking additional doses to make up for those doses that were missed. Instructions on dosing are provided on the Participant Daily Dosing Diary.

At the end of each visit, sites will instruct participants, in writing on the front of the Participant Daily Dosing Diary, when to take their medication prior to their next study visit. This is especially important if the next visit has a collection of blood sample(s) for PK analysis.

Knowing the actual time of dosing is essential for appropriate analysis of samples for TTR stabilization, TTR concentration, and for tafamidis pharmacokinetic measurements. On the day of the study visit, participants will write the actual time that they took their medication in the Participant Daily Dosing Diary and the site staff will record this dosing time in the case report form (CRF).

On Day 1 (Baseline Visit), participants will be instructed to take their first daily dose of 61 mg tafamidis, after the completion of the baseline procedures and to continue dosing capsules each day in the morning (AM dosing) until the next study visit of Month 1 visit. At the end of the clinic visit, the participants will be reminded to take their medication in the clinic, rather than at home, on the day of the next visit of Month 1, as indicated on the Participant Daily Dosing Diary.

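### SAP Appendix 1.1 places TTR samples by days since first dose, so the two Month 1 samples always tie and post-treatment samples can enter visit rows unmarked

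*SAP*

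**What the plan says.** SAP Appendix 1.1 gives one table of day windows for endpoints assessed at Months 1, 6 and 12. Only PK is carved out: "except PK endpoints), the analysis windows are defined in below table". A note in the Month 12 row confirms that PD is covered: "Set upper at Day 375 for PD endpoints". Study day is the collection date minus the first-dose date plus 1, with no clock time and no last-dose term. One value is kept per window: "If two or more visits/observations fall into the same window, the visit / observation closest to the target day should be used". Ties are handled by: "If there is a tie, the later visit should be used".

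Protocol 1.3 (SoA, note h) plans two TTR samples at Month 1: "Month 1 sample: collect pre-dose and at 3 hours (±1.5 hours) post-dose". Protocol 6.1.1 has the Month 1 dose taken in the clinic on the visit day, between the two samples. At the end, the same note says: "Month 12 sample: collect at 1 hour (±30 minutes) post-dose, or End of Treatment sample: collect at time during the clinic visit". Protocol 7.1 and the SoA allow the EOT visit up to 2 weeks after treatment ends. SAP 3.2.3 includes EOT in the PD endpoint, but the window table has no EOT row.

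For PK, SAP 6.2.2 summarizes by visit and nominal time. Appendix 1.1 gives PK its own rows: hour limits for the post-dose samples and, for Month 1 pre-dose, "Prior to dosing of study treatment on the sample collection day".

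**The concern.** The PD rule ignores dosing time, although Protocol 6.1.1 states: "Knowing the actual time of dosing is essential for appropriate analysis of samples for TTR stabilization". Two problems follow.

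- **Month 1.** The pre-dose and 3-hour samples have the same study day, so they are equally far from the target day. They also belong to the same visit, so choosing the later visit does not decide between them. By the SoA, the Month 1 pre-dose sample is the only planned post-baseline TTR sample taken before a dose; the others are at 3, 7 and 1 hours after dosing. If it is dropped, no summary shows stabilization at the end of a dosing interval.
- **EOT.** A sample taken after the last dose, at no set time, is treated like any other sample in its window. It becomes the visit value when the scheduled sample is absent or is no closer to the target day. Visit rows can then mix on-treatment and post-treatment samples without any mark.

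The proportion stabilized is reported with a confidence interval at each post-baseline time point (Protocol 9.4.2), so these rows carry the PD result.

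**Working it through.** **Inputs**
- Participants: at least 53 (Protocol 9.2). The plan's figure reproduces: 1 − 0.97^52 = 0.795 and 1 − 0.97^53 = 0.801, so 53 is the smallest number giving 80%. It is used here only for counting samples.
- PD windows (SAP Appendix 1.1): Month 1 = Days 16–105, target 31; Month 6 = Days 106–270, target 181; Month 12 = Days 271–375, target 361.
- Planned post-baseline TTR samples per participant (SoA note h): 2 at Month 1, 1 at Month 6, 1 at Month 12.
- EOT visit: 0 to 14 days after the last dose.

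**Month 1 tie**
- Both samples fall on study day d, so both distances are |d − 31|. They tie on every possible visit day.
- Planned Month 1 values: 53 × 2 = 106. Planned post-baseline values: 53 × 4 = 212.
- If only the later observation is kept, 53 pre-dose values leave the summaries: 53/106 = 50% of Month 1 and 53/212 = 25% of all planned post-baseline values.

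**EOT sample fills an empty window**
- Final dose Day 150, EOT sample Day 160. No other sample lies in Days 106–270, so this is the Month 6 value, taken 160 − 150 = 10 days after the last dose.
- The earliest scheduled visits under the SoA allowances are Days 24 (31 − 7), 167 (181 − 14) and 347 (361 − 14). If treatment stops before the visit could have taken place, an EOT sample in the window is the only one there. The final-dose days concerned are:

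| Lag from last dose to EOT sample | Month 1 row | Month 6 row | Month 12 row |
|---|---|---|---|
| 14 days | 2–23 | 92–166 | 257–346 |
| 1 day | 15–23 | 105–166 | 270–346 |

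These ranges show when the rule applies. They are not probabilities.

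**EOT sample displaces an attended visit**
- Month 6 sample on Day 175: |175 − 181| = 6. This is within both the SoA allowance of 2 weeks and the 1-week limit in Protocol 8.
- Final dose Day 176, EOT sample Day 183: |183 − 181| = 2. The EOT sample is closer and replaces the on-treatment sample.
- An EOT sample on Day 187 instead: |187 − 181| = 6. This ties, and the later visit, again EOT, is kept.
- The Day 375 cap counts from first dose and prevents none of these cases.

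**Leverage**
- One changed status moves a proportion by 1/n: 1/53 = 1.9 points overall. With 17 participants, the most in NYHA class III or above that the one-third cap in Protocol 4.1 allows among 53, it is 1/17 = 5.9 points. Smaller rows move more.

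**The case against.** **The plan may already intend two Month 1 summaries.** Protocol 9.4.2 and SAP 5.2.1 and 5.2.2 speak of time points, Protocol 8 uses that term relative to dosing, and Appendix 1.1 says it aims to use as much data as possible. This reading is open, and the loss of 53 values depends on the other one. But SAP 6.2 summarizes PD by analysis visit, no nominal times are defined for PD, and the SAP does define them for PK at the same Month 1 times. Two programmers could produce different tables.

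**EOT in the Month 12 position is the protocol's own pairing.** The SoA puts the two in one column, and EOT is part of the endpoint. So EOT values must be reported, and a labelled EOT line does that. The pairing does not justify a Month 1 or Month 6 label.

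**The effect may be small.** Protocol 10.4.1 gives 28 days as the elimination time, so a sample within 14 days of the last dose need not be drug-free. Protocol 2.2.1 expects molar ratios of 3.5 to 9.6 at 80 mg, approaching or on the plateau, and Protocol 4.3 reports comparable Month 1 stabilization effects at 20 and 80 mg. These points lower the likely effect. They do not make the rule correct, and Protocol 2.2.1 also reports greater stabilization above 20 mg.

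**The consequences are limited.** The study tests no hypothesis, PD is secondary, and listed values with recorded times allow a reader to trace a sample. All of this stands.

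**Conclusion.** The concern holds. Followed exactly, the closest-to-target rule can replace an on-treatment TTR sample with one taken after treatment ended, and the tie rule does not say which Month 1 sample to use. The Month 1 tie affects every participant with both samples. The EOT problem can occur but need not: an EOT sample is dropped when an on-treatment sample in the same window is strictly closer to the target day.

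The counts (53 of 106 and 53 of 212) assume 53 participants with all planned samples and the later-observation reading. The effect on percent stabilization, or on the proportion at or above the 32% threshold, cannot be computed, because the documents give no half-life, dropout rate or stabilization rate after stopping. The problem is confined to the PD summary tables, plots and confidence intervals. The primary endpoint and the sample size are not affected. It should be corrected before database lock.

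**What to change.** In SAP Appendix 1.1 and 6.2:

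1. Summarize PD by visit and nominal time, as SAP 6.2.2 does for PK. Give Month 1 separate pre-dose and 3-hour rows, each with its own proportion stabilized and confidence interval, and exempt these two samples from the closest-day and tie rules.
2. Keep PD samples taken after treatment has ended out of the Month 1, 6 and 12 rows. Report them on a separate EOT line with days since last dose.
3. Fix the cut-off for post-treatment before database lock. One option is more than 24 hours, one once-daily dosing interval, after the participant's final dose. The documents set no such limit, so this is a choice to be stated. Counting from the final dose, not the most recent one, leaves the Month 1 pre-dose sample of continuing participants in its row.

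The cost is SAP wording and minor programming. Dose and sample times are already recorded (Protocol 6.1.1 and 8.6), and SAP 6.6.3 already uses the last-dose date. The downside is slightly fewer participants in some visit rows.

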### 1.3. Schedule of Activities (SoA)

The SoA table provides an overview of the protocol visits and procedures. Refer to the **STUDY ASSESSMENTS AND PROCEDURES** section of the protocol for detailed information on each procedure and assessment required for compliance with the protocol.

The investigator may schedule visits (unplanned visits) in addition to those listed in the SoA table, in order to conduct evaluations or assessments required to protect the well-being of the participant.

Procedure/ Assessment	Screening	Baseline visit	Month a					
			1 (±1 week)	3 (Tel eph one visit ±2 weeks)	6 (±2 week s)	9 (Tel eph one visit ±2 weeks)	12 (±2 weeks) (or within 2 weeks after End of Treatment)	Post- treatment follow-up (28+7 days after last dose)
	Day-45 to Day 0	Day 1						
Informed Consent	X							
Medical History	X							
Review entrance criteria	X	X						
Full physical examination	X							
Brief physical examination		X	X		X		X	
Height	X							
Weight	X	X	X		X		X	
12 Lead ECG	X	X	X		X		X	
Vital signs b	X	X	X		X		X	
Echocardiogram	X				X		X	
Tissue biopsy or radionuclide bone scintigraphy (99mTc-PYP) c	X							
Laboratory samples								
Hematology	X		X		X		X	
Serum Chemistry	X		X		X		X	
Coagulation (INR, PT, APTT, FIB)	X		X		X		X	
Thyroid-stimulating hormone, total Thyroxine 4 and free Thyroxine 4		X	X		X		X	
Retinol Binding Protein		X			X		X	
Contraception check d	X			X	X	X	X	X
Pregnancy test (only for WOCBP) e	X				X		X	
Serology (HBsAg, anti- HCV, anti-TP and anti-HIV)	X							
Serum/urine test for primary amyloidosis (AL)	X							

Procedure/ Assessment	Screening	Baseline visit	Month a					
			1 (±1 wee k)	3 (Tel eph one visit ±2 wee ks)	6 (±2 week s)	9 (Tel eph one visit ±2 wee ks)	12 (±2 weeks (or within 2 weeks after End of Treatment)	Post- treatment follow-up (28+7 days after last dose)
	Day-45 to Day 0	Day 1						
Mass spectrometry/ Immunohistochemistry f	X							
Genotyping g	X							
Urinalysis	X		X		X		X	
NT – proBNP, Troponin I		X			X		X	
6-MWT		X			X		X	
TTR stabilization, TTR concentration h		X	X		X		X	
Tafamidis concentrations i			X		X		X	
KCCQ j		X			X		X	
EQ-5D-5L k		X			X		X	
SF-12 k		X			X		X	
NYHA classification	X	X			X		X	
Concomitant treatments	X	X	X	X	X	X	X	
Serious and nonserious adverse event monitoring	X	X	X	X	X	X	X	X
Hospitalization determination		X	X	X	X	X	X	

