### **3.3.2. Electrocardiogram Data**

- Change from baseline in ECG measurements and incidence of electrocardiogram (ECG) abnormalities

12 lead ECG will be measured during screening, baseline, Month 1, 6 and 12. ECG parameters include heart rate, PR interval, QT interval, QTcF interval and QRS interval.

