## **6.3. Other Safety Summaries and Analyses Endpoints**

### **6.3.1. Laboratory Data**

The incidence of laboratory abnormalities observed at any time during the study will be tabulated following Pfizer Reporting Standards. Summary statistics for changes from baseline in RBP will be provided by visit.

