### **6.3.2. Electrocardiograms**

Centrally over-read ECG variables will be summarized by mean change from baseline to each measurement time for heart rate, PR interval, QRS interval, QT interval and QTcF (Fridericia correction) intervals. Additionally, the incidence of categorical increases in QTc intervals will be provided. Categories for QTcF are  $\geq 450$  msec,  $\geq 480$  msec, and  $\geq 500$  msec. Categories for QTcF as change from baseline are  $\geq 30$  msec increase,  $\geq 60$  msec increase and  $\geq 75$  msec increase. QTcF is considered the primary QTc value as this correction is more appropriate. In addition, the number (%) of subjects with normal, abnormal not clinically significant, abnormal clinically significant and unevaluable will also be summarized at each visit.

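### Read as written, the one-ECG-per-window rule can leave a QTcF outlier out of the SAP 6.3.2 category table when another ECG in the same window lies nearer the target day

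*SAP*

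**What the plan says.** **Window rule.** SAP Appendix 1.1 states: "For endpoints with post-baseline assessments at Month 1, 6 and 12 (except PK endpoints), the analysis windows are defined in below table". The windows are Days 16-105 (Month 1, target Day 31), Days 106-270 (Month 6, target Day 181) and Day 271 onward (Month 12, target Day 361). SAP 3.3.2 puts ECG on this schedule: "12 lead ECG will be measured during screening, baseline, Month 1, 6 and 12". The selection rule for two or more observations in one window is that "the visit / observation closest to the target day should be used in the analyses", and then "If there is a tie, the later visit should be used". The appendix mentions ECG by name only to rank the central reading first. The table has no row for End of Treatment.

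**QTcF categories.** SAP 6.3.2 lists absolute categories (at least 450, 480 and 500 msec) and increases from baseline (at least 30, 60 and 75 msec), and says "the incidence of categorical increases in QTc intervals will be provided". It does not say which ECG records count. Protocol 9.4.1.2 is silent too.

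**Defaults and contrast.** SAP 5.2.2 tabulates categorical endpoints by time point. It allows whole-study tables for some of them and gives adverse events as the example. For laboratory data, SAP 6.3.1 is explicit: "The incidence of laboratory abnormalities observed at any time during the study will be tabulated".

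**Where extra ECGs come from.** Protocol 1.3 says "The investigator may schedule visits (unplanned visits) in addition to those listed in the SoA table". Protocol 8.2.3 foresees repeats of abnormal ECGs. Protocol 7.1 places the End of Treatment visit within two weeks after treatment ends, so it can fall in any window.

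**The concern.** Choosing the ECG nearest the target day suits a mean change by visit. It does not suit an outlier count, whose purpose is to show whether a participant ever crossed a threshold. The records most exposed to displacement are those taken off schedule: ECGs prompted by a clinical question, and ECGs taken when treatment stops.

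Protocol 7.1 makes QTcF above 500 msec, or a QTc increase above 60 msec, a reason for withdrawal. Under the window rule, the tracing that led to a withdrawal need not be the one that enters the table. A participant could meet that criterion and be absent from the row for 500 msec or more.

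The loss runs one way. Dropping records can only lower, or leave unchanged, the number of participants counted as ever having crossed a threshold.

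**Working it through.** **The plan's own figure.** The only design figure is 53 participants for an 80% chance of at least one TEAE of 3% incidence (Protocol 9.2). It reproduces: 1 - 0.97^53 = 0.801, and 52 gives 0.795. It concerns TEAEs and is not used below. The documents give no expected rate of QTcF outliers.

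**Rule applied.** An ECG on Day d, in a window with target T, is kept unless another ECG in that window on Day e has |e - T| < |d - T|, or |e - T| = |d - T| with e > d. Days 2-15 belong to no window. All ECGs are assumed to have the same reading status, so the central-reading priority does not decide between them.

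**An example that loses the outlier (hypothetical values).** A normal Month 1 ECG on Day 31, an unscheduled ECG on Day 60 with QTcF 505 msec, and an End of Treatment ECG on Day 65 with QTcF 490 msec. Distances from Day 31 are 0, 29 and 34, so only Day 31 is kept.

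**Examples that keep it.** With earlier visits on target, an End of Treatment ECG on Day 150 is alone in the Month 6 window, and one on Day 300 is alone in the Month 12 window. Both are kept.

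**End of Treatment ECG, earlier visits on Days 31 and 181.**
- Possible days: 32 to 360, or 360 - 32 + 1 = 329.
- Displaced on Days 32-105 (74 days) and Days 182-270 (89 days): 74 + 89 = 163, and 163/329 = 49.5%.
- Kept on Days 106-180 and 271-360.
- With Month 1 moved by up to 1 week and Month 6 by up to 2 weeks (the limits in Protocol 1.3), the share runs from 42.3% to 49.5%. For example, visits on Days 24 and 167 give displacement on Days 39-105 (67) and 196-270 (75), so 142 of 336 days.

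**Unscheduled ECG in a participant with all three scheduled ECGs.** Days 2 to 389 (Day 361 + 28) are 388 days; less the 3 visit days, 385.

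| Scheduled ECG days | Days on which the extra ECG is kept | Displaced or in no window |
|---|---|---|
| 31, 181, 361 | none | 385/385 (100%) |
| 24, 167, 347 | 25-38, 168-195, 348-375 (14 + 28 + 28 = 70) | 315/385 (81.8%) |
| 38, 195, 375 | 25-37, 168-194, 348-374 (13 + 27 + 27 = 67) | 318/385 (82.6%) |

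**Effect on the table.** Each participant missed lowers a row by 1/53 = 1.9 percentage points if 53 are treated.

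**The case against.** The strongest reply is that the SAP never says the QTcF category table uses windowed records. SAP 6.3.2 attaches a time point to the mean changes and a visit to the normal/abnormal counts, but neither to the QTcF categories. The whole-study exception in SAP 5.2.2 is an open list. A whole-study reading is therefore available. This stands as a limit on certainty: use of windowed records is inferred from Appendix 1.1 together with the 5.2.2 default. It does not remove the problem, because no text directs the programmer to the maximum value, whereas the laboratory section does have explicit any-time wording.

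A reader might infer that unscheduled or End of Treatment outliers always vanish. The documents do not support that. An ECG alone in its window is kept, and an outlier at a scheduled visit on or after its target day cannot be displaced by a later ECG. No ECG is scheduled on Days 2-15.

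Other outputs limit the harm. Protocol 7.1 asks for new clinically relevant ECG findings to be reported as AEs. Protocol Appendix 7 lists QTcF prolongation among findings that may qualify as AEs or SAEs. SAP 6.1.1 tabulates TEAEs and lists all AEs. This is fair, but an AE entry does not correct the QTcF table.

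Finally, a maximum over all ECGs could count a faulty tracing that a repeat was meant to disprove. That also stands, and the fix has to handle it.

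**Conclusion.** The concern holds in conditional form. As written, the plan can omit a QTcF outlier from the category table when another ECG in the same window is nearer the target (or ties and is later), or when the ECG falls on Days 2-15. Displacement is the usual result for an unscheduled ECG in a participant with all scheduled ECGs (about 82% of days at the visit-window edges tested, all non-target days when visits are on target). It occurs on roughly half of possible days for an End of Treatment ECG.

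These shares weight every day equally and say nothing about how often outliers occur. The size of any understatement in the reported incidence cannot be given from the documents.

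A reader might also take this as a bias in the primary endpoint, or as a loss of the 80% detection probability. Neither follows. The primary endpoint is TEAE incidence, QTcF categories are placed under other safety endpoints (SAP 3.3.2), and the 3% calculation belongs to TEAEs. The point still deserves correction, because safety is the study's primary objective and the remedy is small.

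**What to change.** In SAP Appendix 1.1 and 6.3.2:

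- Limit the nearest-to-target rule to by-visit summaries.
- Derive the QTcF absolute and change-from-baseline categories from each participant's maximum post-baseline centrally over-read QTcF, over scheduled, unscheduled and End of Treatment ECGs, from first dose to last dose + 28 days.
- Exclude tracings documented as technically invalid, such as lead misplacement shown on repeat.
- Flag any value available only as a local reading, since 6.3.2 specifies central over-reads.

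In SAP 6.3.4, state whether vital sign abnormality counts use the same any-time basis; the section does not say.

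The cost is SAP wording and one derived variable, with no new data collection. There are two downsides: reported outlier rates may look slightly less favourable, and a maximum over more ECGs is more sensitive to measurement noise.
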